## Clinical Investigation Plan

### 5.2.2 Informed Consent

The Investigator or his/her authorized designee (if applicable) will conduct the Informed Consent process, as required by applicable regulations and the center's IRB/EC. This process will include a verbal discussion with the subject on all aspects of the clinical investigation that are relevant to the subject's decision to participate, such as details of clinical investigation procedures, anticipated benefits, and potential risks of clinical investigation participation. Subjects must be informed about their right to withdraw from the clinical investigation at any time and for any reason without sanction, penalty or loss of benefits to which the subject is otherwise entitled. Withdrawal from the clinical investigation will not jeopardize their future medical care or relationship with the investigator.

During the discussion, the Principal Investigator or his/her authorized designee will avoid any improper influence on the subject and will respect subject's legal rights. Financial incentives will not be given to the subject. Subjects may be compensated for time and travel directly related to the participation in the clinical investigation. The subject shall be provided with the Informed Consent form separately that is written in a language that is understandable to the subject and has been approved by the center's IRB/EC. The subject shall have adequate time to review, ask questions, and consider participation. The Principal Investigator or his/her authorized designee will make efforts to ensure that the subject understands the information provided. If the subject agrees to participate, the Informed Consent form must be signed and dated by the subject and thereafter by the person obtaining the consent prior to any clinical investigation-specific procedures. The signed original will be filed in the subject's hospital or research charts, and a copy will be provided to the subject.

Failure to obtain informed consent from a subject prior to clinical investigation enrollment should be reported to Sponsor within 5 working days and to the reviewing center's IRB/EC according to the IRB's/EC's reporting requirements.

If, during the clinical investigation, new information becomes available that can significantly affect a subject's future health and medical care, the Principal Investigator or his/her authorized designee (if applicable) will provide this information to the subject. If relevant, the subject will be asked to confirm their continuing informed consent in writing.

#### 5.2.2.1 Special Circumstances for Informed Consent

The following individual populations will be excluded from participation in this clinical investigation:

- Incapacitated individuals, defined as persons who are mentally ill, mentally handicapped, or individuals without legal authority, are excluded from the study population.
- Individuals under the age of 18 or age of legal consent are excluded from the study population.
- Individuals unable to read or write are excluded from the study population.
- Pregnant or breastfeeding women are excluded from the study population.

All other aspects of the Informed Consent process should be in compliance with **Section 5.2.2**.

### 5.3 Eligibility Criteria

#### 5.3.1 General Eligibility Criteria

Assessment of eligibility criteria is based on review of candidate medical records at the site, an interview with a candidate patient, and determination by the investigator. If the specific tests noted in **Section 5.2.1** (LVEF, LA diameter, and presence of thrombus) were not completed prior to obtaining consent, they

## Clinical Investigation Plan

must be assessed before the subject has an ablation catheter inserted into their vasculature for an ablation procedure.

Patients must meet ALL of the inclusion criteria to be considered for this clinical investigation. If ANY of the exclusion criteria are met, the patient is excluded from the clinical investigation.

### 5.3.2 Inclusion Criteria

- 1) Patient must provide written informed consent prior to any clinical investigation related procedure.
- 2) Documented symptomatic persistent AF, which is defined as continuous AF sustained beyond 7-days and less than 1-year that is documented by (1) a physician's note AND (2) a 24-hour Holter within 90-days prior to the procedure, showing continuous AF, OR (3) two electrocardiograms (from any form of rhythm monitoring) showing continuous AF, with electrocardiograms taken at least 7 days apart
- 3) Refractory or intolerant to at least one Class I or III antiarrhythmic drug (AAD) as evidenced by recurrent symptomatic AF  
Note: Intolerance is defined as unable, unwilling, or refusal to take Class I or III AADs.
- 4) Age 18 years or older
- 5) Able and willing to comply with all pre-, post-, and follow-up testing and requirements

### 5.3.3 Exclusion Criteria

- 1) Continuous AF > 12 months (longstanding persistent AF)
- 2) Previous left atrial surgical or catheter ablation for atrial fibrillation or a previous procedure that required an incision in the left atrium with resulting scar
- 3) Any cardiac procedure (surgical or percutaneous) within 90-days prior to the initial procedure  
NOTE: Diagnostic cardiac procedures in which no intervention, implant, or incision was made in the cardiac tissue are not considered a surgical or percutaneous cardiac procedure.
- 4) CABG surgery within the 6-months (180-days) prior to the initial procedure
- 5) Valvular cardiac surgical/percutaneous procedure (i.e. ventriculotomy, valve repair or replacement and/or presence of a prosthetic or mechanical valve)
- 6) Any carotid stenting or endarterectomy
- 7) Documented or known left atrial thrombus on imaging
- 8) Left atrial (LA) diameter > 50 mm (parasternal long axis view or by CT)
- 9) Left ventricular ejection fraction (LVEF) < 40%
- 10) Unable to take anticoagulation medication due to contraindication or intolerance
- 11) History of blood clotting or bleeding abnormalities
- 12) Myocardial infarction (MI), acute coronary syndrome, percutaneous coronary intervention (PCI) within the 3-months (90-days) prior to the initial procedure
- 13) Documented thromboembolic event (including TIA) within the 12-months (365 days) prior to the initial procedure
- 14) Rheumatic heart disease
- 15) Uncontrolled heart failure or NYHA functional class III or IV

## Clinical Investigation Plan

- 16) Severe mitral regurgitation (regurgitant volume  $\geq$  60 mL/beat, regurgitant fraction  $\geq$  50%, and/or effective regurgitant orifice area  $\geq$  0.40cm^2)
- 17) Awaiting cardiac transplantation or other cardiac surgery within the 12-months (365 days) following the initial ablation procedure
- 18) Unstable angina at the time of the initial procedure
- 19) Acute illness or active systemic infection or sepsis
- 20) AF secondary to electrolyte imbalance, thyroid disease, acute alcohol intoxication, major surgical procedure in the preceding 3-months, or other reversible or non-cardiac cause
- 21) Diagnosed atrial myxoma
- 22) Presence of implanted implantable cardioverter defibrillator (ICD) or cardiac resynchronization therapy-defibrillator (CRT-D)
- 23) Significant pulmonary disease, (e.g., restrictive pulmonary disease, constrictive or chronic obstructive pulmonary disease) or any other disease or malfunction of the lungs or respiratory system that produces chronic symptoms
- 24) Significant congenital anomaly or other anatomic or comorbid medical problem that in the opinion of the investigator would preclude enrollment in this study or compliance with the follow-up requirements or impact the scientific soundness of the clinical trial results
- 25) Pregnant or nursing subjects and those who plan pregnancy during the clinical investigation follow-up period
- 26) Enrollment in an investigational study evaluating another device, biologic, or drug that may interfere with this clinical investigation at the time of the initial procedure or within 30 days prior to the initial procedure
- 27) Presence of any condition that precludes appropriate vascular access or manipulation of catheter
- 28) Life expectancy less than 12-months
- 29) Body mass index  $>$  40 kg/m^2
- 30) Known sensitivity to contrast media (if needed during the procedure) that cannot be controlled with pre-medication
- 31) Renal failure requiring dialysis
- 32) Presence of other medical, social, or psychological conditions that, in the investigator's opinion, could limit the subject's ability to participate in the clinical investigation or to comply with follow-up requirements, or impact the scientific soundness of the clinical investigation results
- 33) History of atriotomy or ventriotomy
- 34) Implanted endocardial left atrial appendage occlusion device

### 5.4 Subject Enrollment

A patient is considered enrolled in the clinical investigation from the moment the patient provides written informed consent and meets all eligibility criteria.

If a TactiCath SE device is used for ablation on an enrolled subject who does not meet eligibility criteria for the trial, they will not be withdrawn from the trial, will be counted in the analysis population and will complete all follow-up requirements.

## Clinical Investigation Plan

### 5.5 Subject Withdrawal

Each enrolled subject shall remain in the clinical investigation until completion of the required follow-up period. However, a subject's participation in any clinical investigation is voluntary and the subject has the right to withdraw at any time without penalty or loss of benefit. Conceivable reasons for discontinuation may include, but not be limited to, the following:

- Death
- Voluntary withdrawal
- Lost to follow-up (described below)
- Subject's following is terminated according to **Section 3.3**

The Sponsor must be notified of the reason(s) for subject discontinuation. The site will provide this information to the Sponsor as documented on the appropriate CRF. Investigators must also report this to their respective IRB/EC as defined by their institution's procedure(s).

No additional follow-up will be required or data recorded from subjects once they are withdrawn from the clinical investigation, except for the status (deceased/alive). If a subject withdraws from the investigation due to problems related to the safety or performance of the device under investigation, they will be followed by their regular physician per their standard of care.

If for any reason, the subject has the TactiCath SE inserted into their vasculature, but no ablation was performed, and the subject will not be rescheduled to receive another ablation procedure, the subject will be followed for 30-days to assess safety and then exited from the trial.

In the event that a subject does elect to withdraw from the trial, the site should make attempts to schedule the subject for a final visit. At this final follow-up visit, the subject will undergo assessments as outlined for an unscheduled visit (**Section 6.7.1**) if the visit does not coincide with a scheduled follow-up visit.

Withdrawn subjects count towards the total enrollment at the site and will not be replaced by enrolling additional subjects.

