#### 4.1.1 Primary Safety Endpoint and Rationale

The rate of device and/or procedure-related serious adverse events with onset within 7-days of any ablation procedure that uses the TactiCath SE catheter (initial or repeat procedure performed  $\leq 180$  days of initial procedure) that are defined below:

- Atrioesophageal fistula
- Cardiac tamponade/perforation

[figure not shown]

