## Clinical Investigation Plan

- Death
- Heart block
- Myocardial infarction (MI)
- Pericarditis
- Phrenic nerve injury resulting in diaphragmatic paralysis
- Pneumothorax
- Pulmonary edema (respiratory insufficiency)
- Pulmonary vein stenosis
- Stroke/cerebrovascular accident (CVA)
- Thromboembolism
- Transient ischemic attack
- Vascular access complications (including major bleeding events)

- 
1. Atrioesophageal fistula, cardiac tamponade/perforation and pulmonary vein stenosis will be evaluated through 15-months.
  2. Pericarditis is a common occurrence for almost all procedures and will only be considered a primary safety endpoint event if the pericarditis pleuritic symptoms last longer than 7-days and/or requires hospitalization of greater than 24 hours for reasons other than for observational purposes only.
  3. Bleeding is a major complication of AF ablation if it requires and/or is treated with transfusion or results in a 20% or greater fall in hematocrit.

[figure not shown]
Definitions regarding these safety events are provided in **Appendix III**.

AF/AFL/AT recurrences that meet the definition of seriousness as noted in **Section 7.1.2** without coexisting conditions (e.g. thromboembolism, worsening heart failure, etc.) will be counted as effectiveness failures but will not contribute to this safety endpoint.

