##### 7.1.1.1 Adverse Event Reporting

Safety surveillance and reporting starts as soon as the patient is enrolled in the clinical investigation (after consent is obtained and all eligibility criteria are met). Safety surveillance and reporting will continue until the last follow-up visit has been performed, the subject is deceased, the subject concludes participation in the clinical investigation or the subject withdraws from the clinical investigation. All adverse event data, including deaths, will be collected throughout the time period defined above and will be reported to the Sponsor on a CRF. Additional information with regard to an adverse event should be updated within the appropriate CRF.

For the purposes of this study, the following adverse events will be reported:

- Adverse events that are assessed by the investigator as being related to either the ablation catheter or the ablation procedure will be reported in the database, preferably within 7-days of the site learning of the event
- Serious adverse events, regardless of relatedness to the procedure and/or the ablation catheter will be reported as described in **Section 7.1.2.1**.

Recurrence of AF, AFL, or AT are not considered reportable adverse events unless they occur in severity, frequency, or other manner that is significantly worse than the subject's baseline condition. Recurrence of AF, AFL, or AT will affect the primary effectiveness endpoint and should be reported on the Follow-Up Visit CRF.

Additionally, urinary tract infections (UTIs) that occur after a procedure and do not require a Foley catheter will not be considered adverse events. UTIs that require a Foley catheter will be reported as AEs if related to the procedure or meet serious criteria.

Unchanged, chronic, non-worsening or pre-existing conditions are not AEs and should not be reported.

All adverse events will be collected on each subject through the 15-month follow-up visit.

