#### 8.2.1 Primary Safety Endpoint Analysis

The primary safety endpoint will be summarized as the percentage of subjects who experienced one or more primary safety endpoints. The primary safety analysis population for the primary safety endpoint will be subjects in the primary analysis population who have completed their 7-day follow-up visit; or crossed the end of the 7-day visit window without the visit but with a primary safety endpoint event. Subjects without an event that are lost to follow up without a visit at or beyond their 7-day follow up visit window will be excluded from this analysis.

The primary safety endpoint event rate will be calculated based on the number of subjects experiencing a primary safety endpoint event divided by the total number of subjects in the analysis population. Relatedness of the event to the catheter and to the procedure will be determined by the independent physician reviewer.

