## Clinical Investigation Plan

### APPENDIX III. DEFINITIONS

The following definitions will be used by the independent, qualified physicians that will determine whether the events listed below constitute a device or procedure related serious adverse event included in the primary endpoint. Most of the definitions have been adapted from the 2017 HRS/EHRA/ECAS/APHS/SOLAECE Expert Consensus on AF Ablation.

[figure not shown]

[figure not shown]
[figure not shown]

[figure not shown]
[figure not shown]
[figure not shown]
[figure not shown]

[figure not shown]

Primary Safety Event	Description
Atrioesophageal fistula	A connection between the atrium and the lumen of the esophagus. Evidence supporting this diagnosis includes documentation of esophageal erosion combined with evidence of a fistulous connection to the atrium, such as air emboli, an embolic event, or direct observation at the time of surgical repair. A CT scan or MRI scan is the most common method of documentation of an atrioesophageal fistula.
Bleeding	Bleeding is a major complication of AF ablation if it requires and/or is treated with transfusion or results in a 20% or greater fall in hematocrit.
Cardiac tamponade/perforation	The development of a significant pericardial effusion during or within 30 days of undergoing an AF ablation procedure. A significant pericardial effusion is one that results in hemodynamic compromise, requires elective or urgent pericardiocentesis, or results in a 1-cm or more pericardial effusion as documented by echocardiography. Cardiac tamponade/perforation should also be classified as “early” or “late” depending on whether it is diagnosed during or following initial discharge from the hospital.
Death	Adverse event resulting in the patient’s death.
Heart block (AV block)	New, persistent 2 nd or 3 rd degree AV block not attributable to a vasovagal reaction or medication effect and requiring permanent pacing.
Myocardial infarction	Irreversible necrosis of heart muscle secondary to prolonged ischemia with at least one of the following three criteria: (2) Detection of ECG changes indicative of new ischemia (new ST-T wave changes or new LBBB) that persist for more than 1 hour; (3) Development of new pathological Q waves on an ECG; (4) Imaging evidence of new loss of viable myocardium or new regional wall motion abnormality.

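### Safety recording stops at withdrawal although three primary safety components run to 15 months, so any such event arising or diagnosed later is counted as no event

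*Combined protocol and SAP*

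**What the plan says.** **Recording after withdrawal.** Section 5.5: "No additional follow-up will be required or data recorded from subjects once they are withdrawn from the clinical investigation, except for the status", meaning deceased or alive. For a subject who withdraws over the safety or performance of the device, the section adds only that "they will be followed by their regular physician per their standard of care". No route for returning information to the study is given. Section 7.1.1.1 lists among the points at which safety surveillance ends that "the subject concludes participation in the clinical investigation or the subject withdraws from the clinical investigation".

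**What is captured up to that point.** The site reports the reason for discontinuation to the sponsor on a CRF. On elective withdrawal, "the site should make attempts to schedule the subject for a final visit", with the unscheduled-visit items of Section 6.7.1, which include adverse events.

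**Endpoint windows.** Section 4.1.1 counts listed events "with onset within 7-days of any ablation procedure that uses the TactiCath SE catheter" (initial, or a repeat within 180 days). Footnote 1 extends three of them: "Atrioesophageal fistula, cardiac tamponade/perforation and pulmonary vein stenosis will be evaluated through 15-months". Appendix III, however, defines tamponade/perforation as "The development of a significant pericardial effusion during or within 30 days of undergoing an AF ablation procedure".

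**Counting rule.** Under Section 8.2.1 the population is "subjects in the primary analysis population who have completed their 7-day follow-up visit", plus subjects past the window without the visit but with an event. Event-free subjects lost with no visit at or beyond the 7-day window are excluded. The rate is subjects with an event divided by subjects in the population. Section 8.7 rules out imputation and specifies censoring only for Kaplan-Meier analyses.

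**The concern.** The endpoint has a 15-month window for three components, but a subject enters the denominator after about one week and can leave observation at any time after that. Between withdrawal and month 15 nothing but vital status is known, and the analysis treats that unknown period as event-free. Because an unrecorded event can only reduce the numerator, the error has one direction.

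The gap also sits awkwardly with the rest of the plan. Section 5.5 gives 30 days of safety follow-up to a subject in whom the catheter was inserted but no ablation was done, while an ablated subject who withdraws is guaranteed none. Section 3.3 keeps device-related events flowing through vigilance reporting if the sponsor stops the study, but Section 5.5 has no counterpart for an individual withdrawal.

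At stake is the credibility of the headline safety rate. The study is descriptive, but Section 1.1.2 says its data will be used with the Persist-End trial to support an expanded indication in China and other Asia Pacific countries.

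**Working it through.** **No planned figure to reproduce.** The endpoints are non-powered (Section 4.0), and the visible text gives no assumed event or withdrawal rate. The check is to follow one subject through the rules and then size the effect on stated assumptions.

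**Tracing a subject.** Take a subject ablated on day 0 who completes the 7-14 day contact, withdraws in week 3 and is later diagnosed with a fistula.

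1. Section 8.2.1: 7-day visit completed, so in the denominator.
2. Section 4.1.1, footnote 1: a fistula within 15 months is an endpoint event if device- or procedure-related.
3. Sections 5.5 and 7.1.1.1: diagnosed after withdrawal, so not recorded.
4. Sections 8.2.1 and 8.7: crude proportion, no imputation, no censoring. The subject counts as event-free.

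**Which components are exposed.** Section 4.1.1 lists 14 components. After a single ablation, 14 - 3 = 11 have a 7-day onset window and are largely settled by the 7-14 day contact. Of the other three:

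- Fistula: exposed to month 15.
- Pulmonary vein stenosis: Appendix III requires CT or MRI confirmation, and Table 2 schedules no follow-up vein imaging. Silent stenosis would be missed in retained subjects too, so the loss specific to withdrawal is symptomatic stenosis.
- Tamponade/perforation: exposed to day 30 under Appendix III or to month 15 under footnote 1. The two passages conflict.

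**Effect of one missed event.** N is about 100 (Section 1.0), so 1/100 = 1 percentage point. Exact (Clopper-Pearson) 95% intervals:

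- 0/100 = 0% (0 to 3.6%) against 1/100 = 1% (0.03 to 5.4%)
- 2/100 = 2% (0.24 to 7.0%) against 3/100 = 3% (0.62 to 8.5%)

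**Expected loss, on assumed inputs.** Let d be the share withdrawn after the 7-day visit, q the late-event risk in those who stay, RR the relative risk in those who withdraw, and f the share of a withdrawn subject's late risk that falls after withdrawal. Then

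- true late rate = (1 - d)q + d·q·RR
- observed late rate = true - f·d·q·RR
- expected events lost = N·f·d·q·RR

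With N = 100, d = 5% (5 subjects) and f = 1 (the least favourable value):

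| q | RR | true late rate | observed | events lost |
|---|---|---|---|---|
| 1% | 1 | 1.00% | 0.95% | 0.05 |
| 1% | 5 | 1.20% | 0.95% | 0.25 |
| 2% | 1 | 2.00% | 1.90% | 0.10 |
| 2% | 5 | 2.40% | 1.90% | 0.50 |

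The late-component rate, not the whole endpoint, is understated by 5% (RR = 1) to 21% (RR = 5) in relative terms. With f = 0.5 these halve to 2.5% and 10%. The chance of missing at least one event among 5 subjects runs from 1 - 0.99^5 = 4.9% to 1 - 0.90^5 = 41%. The expected loss is proportional to the number withdrawn: at 20 subjects it is 20 × 1% = 0.2 to 20 × 10% = 2.0 events.

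**The case against.** Several points on the other side have force.

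- **The triggering problem is not lost.** A reader might infer from Section 5.5 that the safety problem behind a withdrawal disappears. It does not: related adverse events and all SAEs are reportable up to withdrawal, the reason goes on a CRF, and a final visit is attempted. This stands, and it confines the gap to later events.
- **Informative withdrawal is not shown.** A reader might infer that those who leave over the device are the ones most likely to have a late event. That is plausible, but nothing in the documents establishes it or suggests that such withdrawals will be common with a single-use catheter that is not left in place. Hence the range starting at RR = 1.
- **Late tamponade to month 15.** The documents do not clearly support this, given the 30-day definition in Appendix III.
- **The size is small.** The expected loss is below one event on the main assumptions, the intervals at N = 100 are wide, and there is no test or pass/fail criterion. This limits the importance but does not remove a bias that is known in direction and cheap to reduce.
- **Unseen text.** The Section 8.1 definition of the analysis population is redacted and the consent pages are not public, so either might add a rule. Section 8.2.1 nevertheless states its denominator explicitly.
- **Commercial vigilance** may pick up an event with a marketed device, but nothing visible brings it into the study rate.

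**Conclusion.** The concern holds as a limited, one-directional bias. Fistula, symptomatic pulmonary vein stenosis and possibly tamponade arising or diagnosed after withdrawal would be scored as no event for any subject who had completed the 7-day visit. The same counting rule applies to event-free subjects lost to follow-up after that visit. Each missed event costs 1 percentage point at about 100 subjects. The expected loss of about 0.05-0.5 event rests entirely on assumptions (5 withdrawn, 1-2% late risk, relative risk 1-5, all of that risk falling after withdrawal).

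A reader might go further and conclude that the reported rate will be materially wrong, or understated by some definite fraction. The documents do not support that, because they give neither a withdrawal rate nor a late-event rate. The consequence is a possibly too favourable descriptive rate, not a false-positive test result.

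**What to change.** 1. **Sections 5.5 and 7.1.1.1 and the consent form.** Ask each withdrawing subject for permission to keep collecting SAEs and the listed primary safety events, from the subject or the regular physician, through month 15. Record any refusal on the CRF, and state that safety reporting continues where permission is given.
2. **Section 8.2.1.** Alongside the crude proportion, report the 15-month components by Kaplan-Meier or cumulative incidence, censoring at last known safety status, and state the number of subjects without 15-month safety status. This is needed even with the first change, because subjects who refuse or are lost after day 7 would otherwise still count as event-free. It does not replace the first change, since censoring assumes that withdrawal is unrelated to risk.
3. **Section 4.1.1 footnote 1 and Appendix III.** Reconcile the two windows for tamponade/perforation.

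The cost is one brief contact per withdrawn subject, short text changes and a little more analysis with a method the plan already uses in Section 8.2.2. The reported safety rate may become slightly less favourable.
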